13. I hospitalized for a mental health problem in the past 12 months.
14. I am a new patient receiving health services for the first time at this clinic.
15. I am pregnant or planning to become pregnant in the next year [FOR WOMEN ONLY].
16. I am currently breast-feeding [FOR WOMEN ONLY].

GROUP FOUR

17. I am NOT interested in losing unwanted weight at this time.
18. I smoked cigarettes or used e-cigarettes in the last 6 months.

Tracking of Recruitment Progress

The tracking of recruitment, i.e. defining and counting the number contacted and the number interested at each stage and then characterizing enrollees and non-enrollees, is complex. To the extent possible, we will describe the recruitment funnel beginning with the number contacted (denominator). This is most easily accomplished for targeted mailings and, to a lesser extent, for in-person clinic contacts. It cannot be done for those who view a poster, review a notice on a clinic website, or talk to clinic staff. Using the TCC administrative database, we will compare basic characteristics of enrollees to the general population of individuals seeking medical care at the facilities. Using information collected at in-person visits and on the web, we can compare characteristics of enrollees to non-enrollees.

Recruitment of women and minorities

UCLA/TCC investigators have a strong interest and proven track record in recruiting diverse populations. We anticipate that at least 60% of participants will be women, at least 70% will be Latinos and at least 10% will be African American. Given the demographic characteristics of TCC's patients, these goals should be achievable without targeted recruitment efforts.

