8. DATA COLLECTION AND MEASUREMENTS

Data Collection Assessment Periods

Eligibility, baseline and follow-up data will be collected by phone and at in-person visits in the home or in the clinic site waiting room. Intervention process data will be collected separately. In-person data collection visits will be conducted in the waiting rooms of the participating clinics. The following contacts describe the primary data collection points for participant level data.

Prescreen Contacts: During the initial waiting room contact, research staff will provide information about the trial and will collect additional data on eligibility. Those who remain interested and eligible will be consented to participate in the screening phase and will begin to complete screening visit measures. Most patients will complete screening and enrollment activities in this initial visit, some will finish the self-report data assessment but many will be

Patterned after protocol published online in association with Appel et al. (2011)¹⁵

called up for their appointment and therefore will have to leave off completion of the self-report data assessment at a later time. The study participant will be scheduled for an in-person screening visit and will be provided a number to call if interested in asking additional questions.

Screening Visit: Interested persons who are unable to complete screening and enrollment procedures during their first contact will be scheduled at their TCC clinic site from which they were recruited, where their blood pressure, waist circumference, height and weight will be measured. If these measures indicate continued eligibility then the participant will be provided more detail about the trial. Written informed consent to participate in the full trial will be obtained. After consent has been signed, the patient will be randomized and questionnaire data be collected.

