Height (measured)		X	X	X
Waist (measured)		X	X	X
BP (measured)		X	X	X

Patterned after protocol published online in association with Appel et al. (2011)¹⁵

Randomization		X		
Questionnaire topics (administered in this order)				
Demographics/Medical	X	X		X
WHO Health and performance questionnaire		X	X	X
Health-Related QoL-SF-12		X	X	X
Mental Health Inventory (MHI-5)		X	X	X
Physical Activity Quest. (IPAQ)		X	X	X
Physical Activity self-efficacy		X	X	X
Outcomes: hunger – fullness - satisfaction		X	X	X
MyPlate adherence		X	X	X
MyPlate self-efficacy		X	X	X
Weight loss history		X	X	X
Weight control self-efficacy (WEL-SF)		X	X	X
Patient sense of autonomy		X	X	X
Patient satisfaction with care			X	X
Social support and eating habits survey		X	X	X
Social support and exercise survey		X	X	X
TV/Monitor use time		X	X	X
USDA Short-Form Food Security survey		X	X	X
Medical History survey			X	X
Patient satisfaction with weight loss program			X	X
Block Food Freq. Quest.		X		X

*note. F-up-6 = follow-up assessment 6 months after randomization; F-up-12 =follow-up assessment 12 months after randomization.

Principal Measures

The following sections describe the specific measurements to be collected from participants at each contact point in the trial. After considering the total burden of data collection procedures and measurements, we may drop or modify some items. We may also add questionnaires. For example, to improve study procedures and interventions, we will query participants about their experiences in the study.

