Blood Pressure (BP) will be determined via automatic blood pressure cuff using Life Source UA-767 Plus, A&D Medical digital blood pressure monitor. BP will be obtained by trained data collectors according to a standard protocol, adapted from that used in the OmniHeart trial. The cuff size will vary by degree of patient obesity status, with leg cuffs for the most obese. Two measurements (each separated by 1 minute seconds) will be obtained at each visit on the left arm of participants after they have rested quietly in the seated position for at least 5 minutes. A cuff of appropriate size will be identified at the initial visit and used thereafter at all subsequent visits.

Questionnaires (self-report survey items that include weight control self-efficacy, patient quality of life (SF-12), patient satisfaction and patient sense of autonomy previously described)

The trial will collect questionnaire data from participants. These data will be used for a variety of purposes - baseline data to describe participants, outcome data to assess the effects of the trial interventions, and mediating variables to assess potential causal pathways. Questionnaires will be added or removed depending on scientific and logistic considerations, including burden to participants and staff.

Demographic: The demographic questionnaire is a self-report assessment of basic patient characteristics. It assesses age, gender, race/ethnicity, health insurance status, employment, education level, tobacco use, postmenopausal status, and current health conditions (presence of diabetes, hypertension, and cardiovascular disease).

Has a doctor ever diagnosed you with diabetes, heart disease or high blood pressure?
Get medication use from electronic health record, with participant's permission.

MyPlate Adherence Questionnaire: Developed for a previous nutrition intervention trial, the MyPlate Adherence Questionnaire consists of 5 items assessing awareness of the 7 nutrition messages associated with MyPlate and 5 items that assess adherence to five of the 7 MyPlate messages on a typical day (<http://www.choosemyplate.gov/print-materials-ordering/selected-messages.html>). The messages include: 1) Make half your plate fruits and vegetables, 2) Make at least half your grains whole grains, 3) Switch to low-fat or non-fat milk, 4) Choose the foods with lower sodium, and 5) Drink water instead of sugary drinks.

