MyPlate Self-efficacy: Developed for a previous nutrition intervention trial, the MyPlate Self-efficacy scale consists of 5 items querying the participant about her/his confidence that she/he can adhere to the 5 nutrition messages associated with MyPlate (<http://www.choosemyplate.gov/print-materials-ordering/selected-messages.html>)

Physical Activity: The short format, self administered version of the International Physical Activity Questionnaire (IPAQ: <http://ipaq.ki.se>) will be used to assess participants' usual level of moderate to vigorous physical activity. The IPAQ is a standardized self-reported measure of physical activity that has demonstrated validity and reliability.¹⁴¹ It will be used to estimate levels of moderate and vigorous physical activity from the previous week.

Physical Activity Self-efficacy: A 10-item scale was adapted from the 12-item Exercise Self-efficacy scale.¹⁴² Most of the items asked the respondent to indicate how sure she/he was that she/he could stick to the recommended exercise goal despite specific challenges such as when the family demands too much time, there is too much other work to do, when you feel depressed, etc. The test-retest reliability for the 12-item scale was .68; the Cronbach's alpha measure of internal consistency averaged alpha = .85 across two subscales that made up this overall scale.

Depressive Symptoms: The MHI-5 will be used to measure depressive symptoms. The MHI-5 is a five-item mental health Likert measure derived from the SF-36 that was established in 1991.¹³³ Each MHI-5 item has six answer options ranging from 'All of the time' to 'Most of the time' to 'A good bit of the time' to 'Some of the time' to 'A little of the time' to 'Not at all', with a sum score ranging from 5 to 30. High scores indicate good mental health. This measure has been found to be a reliable measure of distress/ mental health.¹⁴³

Health-Related TV viewing time: The NHANES item used to assess typical respondent time spent watching television each day will be used.¹⁴⁴ To assess TV-viewing time, participants were asked: *Over the past 30 days, on average about how many hours per day did you sit and watch TV or videos?* Possible responses included: <1 hour, 1 hour, 2 hours, 3 hours, 4 hours, and > 5 hours. This item was shown to predict obesity status in both children (girls 12y – 18y) and adults (men)¹⁴⁴ and correlated inversely with scores on the Healthy Eating Index.¹⁴⁵

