For patients who may be susceptible to hypotension because they are using medications that lower blood pressure, weight loss interventions have the potential to increase the risk of hypotension. Participants are educated about symptoms of hypotension and urged to contact their PCP if they have symptoms suggestive of hypotension. In addition, staff contact will notify PCP of participants who develop symptomatic hypotension while on anti-hypertensive medications. Changes in blood pressure regimens and overall management of hypertension remain under the control of the participant's PCP.

Cardiovascular Events

All participants with cardiovascular disease (CVD) require approval from their PCP prior to enrolling. PCPs are provided with information about safety guidelines for physical activity for people with CVD. In addition, participants are educated about CVD symptoms and urged to contact their PCP if they have a change in their CVD symptoms. Overall CVD management remains under the control of the participant's PCP. Cardiovascular events are also assessed using a standardized questionnaire at regular, pre-specified intervals. When a staff member learns that a cardiovascular event (including a procedure) has occurred, the physical activity component of the intervention is suspended. The intervention may be resumed after approval from the participant's PCP.

Alert Values

Table 8 lists the alert values and subsequent actions that will occur. In general, the participant, safety officer, and PCP will be notified.

Table 9. Alert Values and Actions

Measure	Alert Value	Notify participant
Blood pressure (avg.)	Level 1 SBP \geq 180mm/Hg OR DBP \geq 110mm/Hg	In clinic. Advise to follow-up with PCP within 1 week
	Level 2 SBP \geq 140mm/Hg OR DBP \geq 90mm/Hg	In clinic. Advise to follow-up with PCP within 1 month.
	Level 3 SBP \leq 70mm/Hg OR DBP \leq 50mm/Hg	In clinic. Advise to follow-up with PCP within 2 months.
PHQ-9 (Depression questionnaire)	Total score \geq 16 & $<$ 21	In clinic. Advise to follow-up with PCP or mental health care provider within 1 month.
	Total score \geq 21	In clinic. Advise to follow-up with PCP or mental health care provider within 1 week

Surveillance and Reporting Procedures

Serious Adverse Events (SAE)

As defined by the Food and Drug Administration, serious adverse events include the following:

- death,
- a life-threatening experience,

Patterned after protocol published online in association with Appel et al. (2011)¹⁵

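### The depression alert in Table 9 is set on the PHQ-9, which nothing in the plan schedules; the scheduled scale, the MHI-5, has no alert value

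*Combined protocol and SAP*

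**What the plan says.** Section 12 (Safety Monitoring) says that staff were ready to act at once on any value meeting the alert table, and that the participant, the safety officer and the primary care provider will generally be notified. The table, captioned Table 9, has three blood pressure levels and two rows for "PHQ-9 (Depression questionnaire". A total of at least 16 and below 21 means in-clinic advice to see the primary care or mental health provider within 1 month. A total of 21 or more shortens this to 1 week.

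Section 8 (Data Collection and Measurements) names a different instrument: "The MHI-5 will be used to measure depressive symptoms". It describes five items with six answer options each and a sum score from 5 to 30, and adds that "High scores indicate good mental health". Table 4 lists "Mental Health Inventory (MHI-5") at baseline, 6 and 12 months. No alert value for it appears anywhere.

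Section 8 also leaves the set of questionnaires open. Under Principal Measures it says "We may also add questionnaires", and under Questionnaires, "Questionnaires will be added or removed depending on scientific and logistic considerations, including burden to participants and staff".

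**The concern.** An alert works only if the measure that triggers it is collected. Here the alert table and the assessment schedule name different depression instruments. Staff following Table 4 would hold an MHI-5 score at each of three assessments with no rule for acting on a poor one. Staff following Table 9 would have a rule but no scheduled score to apply it to.

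What is at stake is participant safety procedure, not inference. The authors evidently wanted a depression score to set off notification and timed follow-up. The mental health item in the exclusion screener (Table 3, section 7) would not do that job. It asks only about admission, "I hospitalized for a mental health problem in the past 12 months", so a participant with marked symptoms who was never admitted passes it.

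**Working it through.** There is no figure in the plan to reproduce. The check is a cross-reference of every measure in Table 9, plus the scheduled depression scale, against Table 4 and the instrument descriptions in section 8.

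| Measure | Alert value in Table 9 | Scheduled in Table 4 | Described in section 8 |
|---|---|---|---|
| Blood pressure | Yes, three levels | Yes: baseline, 6 and 12 months | Yes |
| PHQ-9 | Yes, two bands | No | No |
| MHI-5 | No | Yes: baseline, 6 and 12 months | Yes |

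- Table 4 has 20 questionnaire rows, and none is a PHQ-9.
- Outside Table 9, the PHQ-9 appears only in the abbreviation list.
- Of the 2 measures in Table 9, 1 (blood pressure) has a scheduled input and 1 (PHQ-9) does not.

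A second check asks whether staff could apply the printed cut-offs to the scale they would have in hand. They could not.

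- The MHI-5 sum runs from 5 to 30, which gives 30 − 5 + 1 = 26 possible totals.
- The lower alert band, 16 to 20, would cover 20 − 16 + 1 = 5 of them.
- The upper alert band, 21 to 30, would cover 30 − 21 + 1 = 10.
- The remaining totals, 5 to 15, number 15 − 5 + 1 = 11, and 5 + 10 + 11 = 26.

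High MHI-5 totals mean good mental health. The carried-over rule would therefore give the most urgent follow-up to the 10 best totals and none to the 11 worst. Both cut-offs fall inside the MHI-5 range, so the mistake would not show up as an out-of-range value.

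**The case against.** The strongest defence is that Table 4 is not a closed list. Two clauses in section 8 allow questionnaires to be added. At least one other safety instrument, the Rose Angina Questionnaire named in section 12, is also missing from Table 4. On this view, absence from the table is weak evidence that the PHQ-9 was not to be given. That stands in part: the documents do not show that no PHQ-9 was given, and the point is confined to the written plan. But permission to add a questionnaire does not schedule one, and neither clause names the PHQ-9. The angina case also differs, because there no other instrument is assigned to the construct. For depressive symptoms one is.

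A reader might go further and infer that a participant with a poor MHI-5 score, especially at baseline, has no way of being referred. The documents do not support that:

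- Section 12 provides for a safety evaluation at screening together with the primary care provider, and for Safety Officer review of clinical measures as needed.
- Section 6 allows exclusion at the Principal Investigator's discretion.
- Section 12 also provides for event surveillance at 6 and 12 months, event reports at other contacts, and case review that covers psychological distress.

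These are real safeguards. What they lack is a score that triggers them.

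It is also fair to say that the protocol calls the trial minimal risk and does not list depression among its potential risks. That limits the severity but does not supply the missing input.

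**Conclusion.** The point holds as a mismatch within the plan. The only score-triggered depression alert is set on an instrument that nothing in the plan schedules, and the scheduled instrument has no alert value. It should be fixed, as a safety procedure that cannot run as written. It does not show that safety monitoring is absent, and it does not touch the efficacy analyses.

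The size is 1 of the 2 measures in Table 9. A reader might count 2 of 5 rows, or multiply rows by visits to get a larger share of failed checks. Neither adds information: the two PHQ-9 rows are bands of one score, and Table 9 does not say at which visits the alert applies. The number of participants concerned cannot be estimated, because the documents give no distribution for either scale and no MHI-5 threshold.

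The conclusion rests on reading Table 4 and section 8 as the written schedule, and on no PHQ-9 having been added under the open clauses.

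**What to change.** Make Table 9 and Table 4 agree on one instrument.

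**Preferred.** Replace the two PHQ-9 rows with two low-score MHI-5 thresholds, set by the study clinicians before use, and keep the 1-month and 1-week follow-up times. State that they apply at baseline, 6 and 12 months. Do not carry over 16 and 21. Remove the PHQ-9 from the abbreviation list. Table 9 gives its advice in clinic, but section 8 expects many participants at the initial visit to be "called up for their appointment and therefore will have to leave off completion of the self-report data assessment at a later time". The amendment should therefore allow notification by phone when the score arrives after the visit. The cost is a small amendment, a clinical decision on two cut-offs that the documents do not supply, prompt scoring and some extra referrals. No new visits, participants or questionnaires are needed.

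**Alternative.** Add the PHQ-9 to Table 4 and keep the existing cut-offs. This retains the chosen instrument but adds one questionnaire, with the Spanish translation and cognitive testing that sections 4 and 9 call for. Simply deleting the rows would make the text consistent but would give up the intended safeguard.

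Parts of the protocol are in the past tense. If data collection has ended, the useful step is to report whether a PHQ-9 was given and what was done about poor MHI-5 scores.

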12. SAFETY MONITORING

The study will monitor participant safety. One aspect of safety monitoring is to evaluate potential study participants at screening to determine whether it is safe for them to participate in the interventions. This will be done in collaboration with the participant's PCP, who will have received information and training about the trial, particularly its eligibility criteria, interventions, and safety monitoring procedures. In this trial, primary care will be provided by the participant's PCP, not by study personnel. A second aspect is monitoring the safety of enrolled participants. If a participant develops a medical problem, the safety of continuing or resuming the intervention will be ascertained by the participant's PCP in collaboration with a study clinician. The

Patterned after protocol published online in association with Appel et al. (2011)¹⁵

investigators met weekly during the active intervention phase with the community health workers/ change agents to discuss, among other things, evidence of adverse events. Surveillance for serious adverse events and other relevant clinical events occurred as needed. Third, if we became aware of medical problems from abnormal physical measurements, such as blood pressure assessment, we referred the patient to her primary care physician and follow-up to make sure that she completed the referral. Results of routine physical measures obtained as part of study visits will be provided to the participant's PCP with patient's consent. In addition, the staff were prepared to address immediately items meeting the criteria for 'Alert Values' listed in the table below. A designated study clinician with appropriate expertise will be designated as the 'Health Safety Officer' and will review medical eligibility criteria and clinical measures as needed. The Safety Officer will also be responsible for reviewing and reporting SAEs for the site, as detailed elsewhere. This person or persons will have appropriate back-up during vacations or other absences to provide 24/7 medical safety coverage for the duration of the study.

Potential Risks

The following sections describe potential risks associated with the study along with procedures to minimize risk.

Physical Activity

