We recognize the need to minimize the potential risks of physical activity in previously sedentary individuals with CVD risk factors. During the screening process, we will exclude persons with a CVD event within the past 6 months. In screenees with a prior CVD event (over 6 months ago), diabetes, peripheral vascular disease, or a positive Rose Angina Questionnaire, PCP approval is required specific to the patient's CVD risk. In order to protect the participants' safety, we will continuously reinforce our recommendation to engage in moderate-intensity physical activity. We will also recommend a safety evaluation by their PCP for those participants who wish to progress to vigorous physical activity. Still, it is important to acknowledge the participant's autonomy. We can recommend that participants follow safety advice but cannot force them to do so.

Nutrient Intake

Calorie restriction can theoretically lead to inadequate nutrition or excessive, rapid weight loss. To minimize these risks, participants are encouraged to eat a variety of foods from all food groups and to maintain an adequate calorie level. 6 month follow-up to check that patients are not suffering excessive weight loss. Participants will be advised that marked and sustained caloric restriction can have serious health risks, e.g. gallstones and/or cholecystitis.

Hypoglycemia Related to Exercise and Lifestyle Interventions

For patients who may be susceptible to hypoglycemia due to use of anti-diabetic medications, weight loss interventions have the potential to increase the risk of hypoglycemia, especially during the time when diet and/or physical activity interventions are implemented. To minimize the risk of hypoglycemia, we will require PCP approval prior to enrolling individuals with diabetes. PCPs are provided with relevant information, prepared by the study clinicians. In addition, participants are educated about symptoms of hypoglycemia. They are urged to contact their PCP if they have symptoms or blood glucose values suggestive of hypoglycemia. Changes in diabetic regimens and overall management of diabetes remain under the control of the participant's PCP.

Symptomatic Hypotension Related to Exercise and Lifestyle Interventions

Patterned after protocol published online in association with Appel et al. (2011)¹⁵

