- inpatient hospitalization or prolongation of existing hospitalization,
- a persistent or significant disability/incapacity, or
- a congenital anomaly/birth defect.

Important medical events that do not result in death or require hospitalization may be considered serious adverse events if they jeopardize the participant's health or require medical or surgical intervention to prevent one of the outcomes in the definition. Surveillance for serious adverse events and other relevant clinical events that may be associated with study participation will occur at in-person visits scheduled at 6 months and 12 months after randomization. This is done using a standardized questionnaire. In addition to the fixed time points, participants may report events in other settings, e.g. phone and intervention contacts. These events will be referred to unmasked staff that will gather relevant information and complete the standardized questionnaire. A study clinician will review the completed forms, will classify the event according to several dimensions (expectedness, relatedness, and type), and will take appropriate action. Safety-related events will be reported in a timely fashion as required by the Safety officer, the IRB, and PCORI.

Expected Events

Over the duration of the trial, which could last up to six months, a number of medical events may be expected to occur in obese adults, including routine surgeries and procedures, the development of cancer or other chronic conditions, increased symptoms from a chronic condition, musculoskeletal problems, motor vehicle accidents, and other types of accidents (e.g. falls, acts of violence).

Pregnancy and Other Exclusions

If a participant becomes pregnant during study after enrollment she is then excluded. If a participant develops cancer, unstable angina, or another condition for which weight loss or exercise might be contraindicated, further participation will be determined by the participant's PCP in conjunction with a study clinician.

Data Safety and Monitoring Plan

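### Before month 6 the plan schedules no general structured adverse-event question; one brief item in the existing calls and home visits would make early capture active at small cost

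*Combined protocol and SAP*

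**What the plan says.** Section 12 (Surveillance and Reporting Procedures) states that surveillance for serious adverse events and other relevant clinical events "will occur at in-person visits scheduled at 6 months and 12 months after randomization", using a standardised questionnaire. Table 4 in Section 8 puts the medical history survey at the same two visits. Between visits, "participants may report events in other settings, e.g. phone and intervention contacts"; unmasked staff then complete the same questionnaire and a study clinician classifies the event.

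Other provisions operate before month 6:

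- Investigators meet the coaches weekly during the active phase "to discuss, among other things, evidence of adverse events", and the study team reviews adverse events weekly (Section 12).
- Coaches and the Intervention Director hold weekly case management on clinical issues (Section 11).
- The Health Safety Officer role is to "provide 24/7 medical safety coverage for the duration of the study".
- Participants are taught the symptoms of hypoglycaemia, hypotension and cardiovascular disease and told to contact their primary care provider. Staff notify the provider of symptomatic hypotension in participants on antihypertensive drugs.
- "Cardiovascular events are also assessed using a standardized questionnaire at regular, pre-specified intervals". The intervals are not given.

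On timing of risk, Section 12 says hypoglycaemia may increase "especially during the time when diet and/or physical activity interventions are implemented". Table 7 places all 11 contacts (7 calls, 2 home visits, 2 group sessions) in months 1 to 3. Section 11 says a REDCap system drives the calls and leader guides structure each type of contact.

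On weight, Section 12 states: "Calorie restriction can theoretically lead to inadequate nutrition or excessive, rapid weight loss". The check it names is a "6 month follow-up to check that patients are not suffering excessive weight loss". Table 9 has alert values for blood pressure and the PHQ-9 only.

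**The concern.** By the plan's own account, part of the risk is concentrated while participants are changing diet and activity. In that period no general event question is specified for every participant. The weekly meetings and case management can act only on what participants volunteer or coaches notice. An early event that is not volunteered waits for the 6-month questionnaire and then depends on recall.

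What is at stake is how promptly and completely early events are captured. Section 3, Part B says the trial will address the benefits and harms of each option, and the description of harms before month 6 would rest mainly on volunteered reports and recall. The contacts that could carry a question already exist and are already scripted.

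**Working it through.** **Contacts.** Table 7 gives 2 home + 2 group + 7 telephone = 11, and by month 4 + 4 + 3 = 11, so the plan's total is reproduced. Calls plus home visits are 7 + 2 = 9 per participant: 3, 4 and 2 in months 1, 2 and 3, and none in months 4 to 6.

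**Scheduled general event questions before month 6.** Now 0; with an item at calls and home visits, 9 at full attendance.

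**Mean wait to the next general structured question.** Assumptions: events uniform over weeks 0 to 26; contacts evenly spaced over 13 weeks in Table 5 order, so spacing is 13/11 = 1.182 weeks (squared, 1.397); the question is not asked at the group sessions (contacts 3 and 9). With gaps g between questions, mean wait = Σ(g²/2)/26.

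| Scenario | Sum of g²/2 | Mean wait (weeks) |
|---|---|---|
| Present plan | 26²/2 = 338 | 13.0 |
| All 11 sessions attended | 15 × 1.397/2 + 13²/2 = 10.5 + 84.5 = 95.0 | 3.65 |
| First 6 sessions only (5 asked) | 8 × 1.397/2 + 18.91²/2 = 5.6 + 178.8 = 184.4 | 7.1 |
| First 2 sessions only | 2 × 1.397/2 + 23.64²/2 = 1.4 + 279.4 = 280.8 | 10.8 |
| No sessions | 338 | 13.0 |

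The factors 15, 8 and 2 are the sums of squared gaps in units of one spacing; at full attendance the gaps are 1, 1, 2, 1, 1, 1, 1, 2, 1. Table 7's 4/4/3 monthly spacing gives 3.68 instead of 3.65. Section 3 also lets sessions run up to the 6-month assessment. If all were spread evenly over 26 weeks, the spacing would be 26/11 = 2.364 and the wait 15 × 2.364²/2/26 = 1.6 weeks.

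**Months 0 to 3 alone**, where the plan locates the implementation period: the present mean wait to the 6-month visit is 6 − 1.5 = 4.5 months. With questions at 3, 4 and 2 evenly spaced contacts per month and full attendance it is (3 × (1/3)² + 4 × (1/4)² + 2 × (1/2)²)/2/3 = 1.083/6 = 0.18 months. For months 3 to 6 the wait stays at 1.5 months on the planned schedule.

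**Coach time.** 261 × 9 = 2,349 contacts. At an assumed 1, 2 or 3 minutes each this is 39, 78 or 117 hours. Per participant it is 9 to 27 minutes, against 7 × 15 + 2 × 50 = 205 to 7 × 20 + 2 × 60 = 260 minutes of call and home-visit time already planned, or about 3.5% (9/260) to 13% (27/205).

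**The case against.** The strongest reply is that the gap may not exist in practice. The call scripts, leader guides and fieldwork manual are not in the documents and could already contain an event question; only its absence from this text is shown. Section 12 also rates the trial as minimal risk and scales monitoring to that. Table 3 screens out current insulin users, and diabetes or cardiovascular disease requires the primary care provider's approval. The wait times measure delay to a question, not to detection, and the documents give no event rate or volunteering rate. All of this stands. It limits the size of the point and makes the fix conditional on what the scripts hold.

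Three stronger readings are tempting, and the documents do not support them.

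- **That safety goes unmonitored before month 6.** The weekly meetings, case management, round-the-clock coverage and symptom education are real. Early cardiovascular ascertainment is unclear, because the interval is unstated, rather than shown to be absent.
- **That rapid weight loss has no route to anyone before month 6, so a weight row is needed in Table 9.** Coaches calculate weight change at each call. Weekly weight reporting is planned in the first few weeks for calorie counting and in months 1 to 3 for MyPlate (Section 11). Calorie goals in the calorie-counting arm are reviewed after each session. Case management and the weekly adverse-event meetings give an observed loss a path to investigators. Only a stated threshold is missing. Call weights are also participant-reported, whereas baseline is a duplicate reading on a calibrated clinic scale (Section 8), so scale and clothing differences could create or hide a loss.
- **That the change would improve the comparison of harms between arms.** Coaches are unmasked and differ by arm (Sections 10 and 13), so events they solicit should not enter that comparison.

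**Conclusion.** The point holds as a modest, optional improvement. The documents specify no general structured event question between randomisation and month 6, and early capture rests mainly on volunteered reports and staff observation. Under uniform events and Table 7 scheduling, a question at nine existing contacts would cut the mean wait from 13 weeks to about 3.7 at full attendance and 7.1 if only the first six sessions are attended. Section 14 calls early drop-out particularly common, so the full-attendance figure is a best case. Non-attenders gain nothing, and months 4 to 6 stay uncovered unless sessions run late. The gain is in timeliness and completeness of early capture. How many events it would affect cannot be estimated from the documents.

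**What to change.** - Add one brief standard question to the 7 REDCap-driven calls and 2 home visits in both arms, unless the scripts already hold one: any hospitalisation, cardiovascular event or procedure, or symptoms of hypoglycaemia or hypotension since the last contact. Send positive answers to the clinician review already set out in Section 12.
- Keep the masked 6- and 12-month questionnaire as the only between-arm comparison of events, and state when the cardiovascular questionnaire is given.
- Optional and secondary: let a large reported weight loss prompt a confirmatory clinic weight and notice to the Health Safety Officer, at a threshold the officer sets. A reported weight should not itself count as an alert value.
- If contacts have ended, as past-tense passages in Sections 3 and 12 suggest, report that events before month 6 were mainly passively ascertained.

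The cost is the coach time worked out above, an edit to the call system and leader guides, and some clinician review that cannot be sized without an event rate. No new visits are needed. The drawback is more events recorded by unmasked coaches.
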